Enrollment to this study was halted on 20-Nov-2015. Based on the small number of patients enrolled prior to the enrollment halt, the primary endpoint will not be obtained and therefore it is no longer necessary for patients to continue to receive placebo. With this in mind, ongoing patients will be unblinded in order to permit crossover to LEE011 for those patients receiving placebo.

Other changes implemented in this amendment:

[figure not shown]
- To update the preclinical safety pharmacology and toxicology sections to include recent data on teratogenicity of LEE011.
- To correct minor typographical and grammatical errors throughout the document.

Study status:

The CLEE011X2201 study started enrollment on 26-February-2015. Enrollment to this study was halted on 20-Nov-2015. Prior to recruitment halt, a total of 10 patients were enrolled. As of 18-Aug-2017, there are 4 patients on treatment, 3 of which are blinded and 1 has crossed over to LEE011 treatment.

Changes to the protocol

- Section 1.2.1.3 – updated preclinical safety pharmacology and toxicology
- Section 4.1 – revised treatment procedures after early study termination
- Section 4.1.2 – added language to facilitate unblinding of ongoing patients and allow placebo patients to crossover to LEE011 treatment if the investigator believes it is in the best clinical interest of the patient
- Section 4.1.3, 4.1.4 and 4.1.5 – revised follow-up procedures after early study termination
- Section 4.1.6 – revised crossover treatment procedures after study termination and following patient enrollment to a LEE011 rollover clinical trial (CLEE011X2X01B)
- Section 4.3 – added language to permit patient rollover to CLEE011X2X01B
- Section 4.3 – revised to align with Section 10.4 regarding when a primary CSR will be produced
- Section 7.1.3 – added transfer to a LEE011 rollover clinical trial (CLEE011X2X01B) as a reason for end of treatment
- Section 7.1.3 – changed parent/guardian decision to patient/parent/guardian decision

- Section 7.1.5.1 – revised follow-up procedures following patient enrollment to a LEE011 rollover clinical trial (CLEE011X2X01B)
- Section 7.1.5.2 and 7.1.5.3 – revised follow-up procedures after early study termination
- Section 10 – revised to clarify CSR reporting after early study termination or patient enrollment to a LEE011 rollover clinical trial (CLEE011X2X01B)

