2.2 Rationale for the study design

This is a randomized double blind (investigator and patient), placebo-controlled, phase II study of LEE011 in patients with progressive relapsed/refractory teratoma for whom standard therapeutic options are not available. The two-arm randomized design minimizes allocation bias, balancing both known and unknown prognostic factors in the assignment of treatment. Blinding will minimize the risk of overstating LEE011 effect. Given the variable growth rate of teratomas, documentation of radiologic progression within 12 weeks prior to enrollment (compared to a prior scan within 1 year) will be required.

A placebo-controlled design with crossover, at time of documented disease progression per RECIST v1.1, permits a more objective assessment of clinical improvement and radiologic response, while at the same time permitting all enrolled patients access to LEE011. There is no accepted standard therapy for patients eligible for enrollment in this study and case reports of individualized regimens are discouraging ([van der Gaast et al 1991](#), [Ornadel et al 1995](#), [Rustin et al 1984](#)). Patients will be randomized 2:1 to the experimental arm in order to

increase the probability of patients receiving active drug upfront and maximize collection of safety data. The presence of a placebo arm will also help to facilitate the evaluation of whether adverse events are related to LEE011. The use of a cross-over design will impact the ability to provide a robust estimate of overall survival, which is acceptable given the exploratory nature of this phase II study.

Preclinical and clinical studies suggest that the vast majority of teratoma have pRB ([Bartkova et al 2003](#)); therefore, pre-screening for pRB status will not be required but will be assessed retrospectively.

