## **1 Introduction**

[figure not shown]
This document describes the detailed statistical methodology for the Report Analysis Plan (RAP) of study CLEE011X2201 Protocol Amendment 2. The data will be analyzed by Novartis and/or designated CRO. It is planned that the data from all centers that participate in this protocol will be used.

The purpose of the CSR is to report the assessment of clinical efficacy and safety of the LEE011 in patients with relapsed, refractory, incurable teratoma with recent progression.

The list of tables to provide at each analysis will be detailed in Module 7.

All changes to the planned analysis described in Modules 3, 7 and 8 required before or after database lock will be made through an amendment or an addendum, respectively. Note that obvious corrections will be made at the time of analysis to address minor formatting or spelling mistakes present in RAP modules without the need to amend these modules.

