### **2.1.2.6 On-treatment assessment/event**

Safety summaries and selected summaries of deaths will summarize only on-treatment assessments/events. On-treatment assessment/event is defined as any assessment/event obtained in the time interval:

Date of first administration of study treatment through the date of last administration of study treatment + 30 days, i.e. including the lower and upper limits. (Note: However, the calculation of study treatment duration may use different rules as specified in [Section 3.3.1.1.](#))

Adverse events that begin or worsen after informed consent should be recorded in the Adverse Events CRF. Conditions that were already present at the time of informed consent should be recorded in the Medical History page of the patient's CRF.

If the last date of study treatment is missing, on-treatment assessments/events include any assessment/event recorded in the database and which occur after the start date of study treatment.

Data listings will include all assessments/events, flagging those which are not on-treatment assessments/events.

Note: The date of first administration of study treatment in the randomized treatment phase and the date of last administration of study treatment in the randomized treatment phase are defined in [sections 2.1.3.1](#) and [2.1.3.2](#), respectively.

For patients who crossed over to LEE011, the placebo group will include all events before the date of first administration of LEE011 and will not include the 30 days are described above. While the LEE011 crossed over group will include all events after the date of first administration of LEE011 and will include the 30 days.

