#### **3.6.1 Adverse event**

Adverse events are coded using the Medical Dictionary for Regulatory Activities (MedDRA) terminology. Although CTCAE version 4.03 grading is by definition a 5-point scale generally corresponding to mild, moderate, severe, life threatening and death, CTCAE grade 5 (death) will not be used since this information will be collected on the “End of Treatment”, “Study evaluation completion” or “Survival information” CRF pages.

Separate summaries and listing for adverse events (AEs) and serious AEs (SAEs) recorded during the study, and all death (on-treatment and post-treatment, with appropriate flag variable to identify on-treatment death) will be provided. Additional summaries and listing based on the relationship to study drug by treatment, study drug discontinuation, requiring dose adjustment or delay will be produced. Listing and summaries will be produced according to the following rules:

- Patients reporting and experiencing multiple occurrences of a specific AE will have occurrences listed but will be counted only once in the appropriate event category/class and according to the worst observed grade within summary tables.
- AEs will be summarized by presenting the number and percentage of patients having at least one AE, and having at least one AE in each primary system organ class and for each preferred. AE will be sorted by descending frequency or alphabetically (system organ class [SOC] and preferred term [PT]).

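### No adverse-event window ends at the Amendment 3 unblinding, so open-label reports from up to 3 of 10 patients would be pooled with blinded data, mainly in the LEE011 column

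*Protocol*

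**What the plan says.** - **Unblinding.** The Amendment 3 rationale (18-Aug-2017) explains that the primary endpoint will not be obtained, and so "ongoing patients will be unblinded in order to permit crossover to LEE011 for those patients receiving placebo". The trigger is the halt in enrollment, not progression. Whether an unblinded placebo patient then crosses over is left to the investigator's judgment.
- **Numbers.** Under Study status, "a total of 10 patients were enrolled" before recruitment stopped on 20-Nov-2015. On the amendment date, "there are 4 patients on treatment, 3 of which are blinded and 1 has crossed over to LEE011 treatment".
- **SAP version.** SAP Section 1 gives the "statistical methodology for the Report Analysis Plan (RAP) of study CLEE011X2201 Protocol Amendment 2". Its last update is dated 07-Dec-2016.
- **Window.** SAP 2.1.2.6 defines on-treatment as "Date of first administration of study treatment through the date of last administration of study treatment + 30 days". Protocol 10.5.3.1 uses the same period.
- **Columns.** SAP Section 3 defines three groups: (a) randomized placebo until the switch to LEE011 or discontinuation, (b) randomized LEE011 with no time limit, and (c) crossover patients from first LEE011 dose. Only (a) and (b) get summary tables. SAP 2.1.2.6 and 3.6 repeat the placebo cut at first LEE011 dose.
- **Causality.** SAP 3.6.1 plans "Additional summaries and listing based on the relationship to study drug by treatment". Protocol 8.1.1 makes relatedness a yes/no judgment.
- **Existing separation rule.** Protocol Section 10 lists LEE011 data collected after progression and does not pool them with earlier data.

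**The concern.** Whether an AE is reported, how it is graded and whether it is called related can all be influenced by knowing the treatment. From the code-break date the investigator has that knowledge, yet the planned tables make no distinction between events before and after it. The two arms are also handled unequally. A LEE011 patient who continues stays in the comparative column, while a placebo patient who crosses over leaves it.

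The comparison matters to this trial's own reasoning. Protocol 2.2 says "The presence of a placebo arm will also help to facilitate the evaluation of whether adverse events are related to LEE011", and the safety objective is framed as LEE011 compared with placebo. SAP Section 4 drops the PFS and secondary efficacy analyses, so the by-treatment AE tables are the main comparative output left. A mixture of blinded and open-label causality calls weakens the placebo arm's contribution to those tables.

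**Working it through.** The plan gives no figure for this point, so the check is a reading of the rules followed by bounds on the patient counts.

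**1. What happens to events after the code break**

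| Patient after unblinding | Leaves the by-arm tables at | Open-label time in the tables |
|---|---|---|
| LEE011, continues | last dose + 30 days | all of it, LEE011 column |
| Placebo, crosses over | first LEE011 dose | code break to first LEE011 dose, placebo column |
| Placebo, does not cross over | last dose + 30 days | all of it, placebo column |

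No row is cut at the code break. The only rule that separates late LEE011 data (Protocol Section 10) starts at progression, so it does not reach a LEE011 patient unblinded without progression. SAP group (b) does not state even that cut.

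**2. Timing.** From 07-Dec-2016 to 18-Aug-2017 is 254 days, so the SAP predates the amendment. Protocol 9.4 still describes codes being opened after database lock. Protocol Section 10 sends all data before termination to a final CSR if no CSR has yet been reported.

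**3. How many patients.** On treatment: 3 blinded + 1 crossed over = 4, as stated. At most 3 of 10 can add newly open-label data under Amendment 3.

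**4. Share of the LEE011 column.** The arm split is not given. The 2:1 ratio gives an expectation of 10 × 2/3 = 6.7 on LEE011, so 6, 7 and 8 are taken as assumptions. The crossed-over patient was on placebo, which leaves 9 patients from whom the 3 blinded come.

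| On LEE011 (assumed) | Placebo among the other 9 | Blinded patients who can be on LEE011 | Share of column |
|---|---|---|---|
| 6 | 3 | 0 to 3 | 0/6 to 3/6 = 0% to 50% |
| 7 | 2 | 1 to 3 | 1/7 to 3/7 = 14% to 43% |
| 8 | 1 | 2 to 3 | 2/8 to 3/8 = 25% to 38% |

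If the 3 are treated as a random draw from the 9, the chance that at least one is on LEE011 is 1 − 1/84 = 98.8% with 6 on LEE011 (84 being the number of ways to choose 3 from 9). It is 100% with 7 or 8.

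**5. Share of each patient's time.** Enrollment ran from 26-Feb-2015 to 20-Nov-2015, so by 18-Aug-2017 each of the 3 had been enrolled for 637 to 904 days (about 21 to 30 months). For an assumed open-label stretch of m months the share is 30.44m / (d + 30.44m), with d = 904 or 637:

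- 1 month: 3% to 5%
- 3 months: 9% to 13%
- 6 months: 17% to 22%
- 12 months: 29% to 36%

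**6. When a late report changes a table.** SAP 3.6.1 counts a patient once per event, at worst grade. A post-unblinding report therefore matters only if it brings a new term, a higher grade or a new relatedness call.

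**The case against.** The strongest reply is that little depends on this. The output is a short close-out report on 10 patients, and the visible SAP plans no inferential AE comparison. At most 3 patients are affected, each after about 21 months or more, when many of their AE terms may already have been counted. Amendment 3 also lets LEE011 patients transfer to the rollover trial, and Protocol 7.1.5.1 exempts them from the 30-day safety evaluation, so the open-label stretch could be short. All of this stands as a limit on size. It does not supply the missing rule.

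Four stronger readings are tempting, and the documents do not support them:

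- A reader might infer that open-label data enter one arm only. They do not: placebo time between code break and first LEE011 dose, or without crossover, stays in the placebo column.
- A reader might infer that an out-of-date SAP is the whole cause. Protocol 10.5.3.1, in the Amendment 3 version, has the same window, so simply aligning the SAP with the current protocol would change nothing.
- A reader might infer that the crossover group already has a separate table column to copy. SAP Section 3 gives that group listings only.
- A reader might take one patient's weight in the LEE011 column (1/8 = 12.5 to 1/6 = 16.7 percentage points) as the size of the bias. That weight applies equally to blinded events and measures no bias.

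**Conclusion.** The point holds as a gap in the rules. Neither the SAP nor Protocol 10.5.3.1 ends the comparative AE window at the unblinding, so open-label reports and causality calls from up to 3 of 10 patients would be pooled with blinded data, mainly in the LEE011 column.

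The size and direction of any bias cannot be computed. A reader might infer that the tables are biased against LEE011. That is plausible, but the documents show no event data, no arm split and no open-label duration. Two further steps are inferences: that unblinding precedes database lock, since no lock date is given, and that at least one of the three blinded patients is on LEE011, which is very likely under the assumptions above. The text of Protocol Sections 4.1 to 4.1.6 is not available for review, so the unblinding procedure itself could not be checked.

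This is an inexpensive improvement to a descriptive output. It does not invalidate the report.

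**What to change.** In SAP 2.1.2.6, Section 3 groups (a) and (b), and Section 3.6, end the window for the by-arm AE and related-AE tables, in both arms, at the earliest of:

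- last dose + 30 days;
- first crossover dose of LEE011;
- the date the patient's code was broken.

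Keep the Protocol Section 10 rule that LEE011 data after progression are not pooled, and state it in the SAP. Show later on-treatment events separately as open-label data and flag them in the listings. Record the change in SAP Section 4 as a departure from Protocol 10.5.3.1, since the protocol carries the longer window.

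The cost is a short SAP amendment and one date per patient. Protocol 8.3 runs emergency code breaks through the IRT. That the Amendment 3 unblinding is recorded there too is an assumption to confirm. The downside is that a few late events leave the comparative columns, though all of them remain reported.

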1.1 Overview of disease pathogenesis, epidemiology and current treatment

1.1.1 Disease pathogenesis

Teratomas consist of cell types derived from one or more of the germ layers (mesoderm, endoderm and ectoderm) and arise most commonly in the gonads or midline structures including the anterior mediastinum, retroperitoneum, sacrococcygeal region, and the pineal gland. Teratoma classification is dichotomized into benign and malignant. Benign teratomas are distinguished as mature or immature based on the proportion of differentiated tissue observed. Malignant teratomas include mature/immature teratomas that have metastasized or contain non-germinal malignant patterns (malignant transformation) such as carcinoma or sarcoma ([Gatcombe et al 2004](#)). Teratomas may also arise within other germ cell tumor (GCT) types, most commonly non-seminomatous germ cell tumors (NSGCT). Metastatic sites of NSGCT often contain teratomatous elements at diagnosis ([Sheinfeld et al 2003](#)).

Deregulation of the retinoblastoma tumor suppressor pathway in GCT has been well documented ([Bartkova et al 2003](#)). In the non-diseased state, cell cycle progression from G₁→S is initiated by sequential phosphorylation at different sites of retinoblastoma protein (pRB) by both cyclin D-CDK4/6 complex and cyclin E-CDK2 complex and the subsequent release of bound E2F. The phosphorylation events mediated by CDK4/6 are prerequisites for those catalyzed by CDK2 ([Bartek et al 1997](#)). Upregulation of CDK4 and cyclin D2 is believed to be a central event in GCT tumorigenesis ([Houldsworth et al 1997](#), [Schmidt et al 2001](#)). Although pRB expression is absent or grossly reduced in undifferentiated GCT, more differentiated NSGCT such as teratocarcinomas and teratomas demonstrate strong expression of pRB ([Strohmeyer et al 1991](#), [Bartkova et al 2003](#)).

1.1.2 Epidemiology

[figure not shown]
[figure not shown]
Malignant teratoma is rare in both pediatric and adult populations. Review of the Surveillance, Epidemiology, and End-Result (SEER) data revealed an incidence of 0.14/100,000 women-years with 531 cases identified over the 30 year period reviewed from 1973-2002 ([Smith et al 2006](#)). The frequency is higher in males. Growing Teratoma Syndrome (GTS), develops during or after treatment in about 2-7% of male patients with NSGCTs ([Andre et al 2000](#)). The US incidence of testicular GCT is 5.7/100,000 males (7,920 cases in 2013, SEER), this translates to about 355 cases of GTS annually. The incidence of testicular cancer is similar in Western Europe and Australia, but comparatively low in Asia and Africa at 1/100,000 males.

[figure not shown]
1.1.3 Current treatment

[figure not shown]
Unlike NSGCTs which are sensitive to cytotoxic chemotherapy, teratomas are highly chemoresistant and optimally treated by complete surgical resection ([Speiss et al 2007](#)). More than 80% of cases of GTS are successfully managed by surgical resection. However, no standard therapy exists for progressive, unresectable teratoma in adult or pediatric patients ([Andre et al 2000](#)). Case reports of efficacy with various agents including interferon ([van der Gaast et al](#)

1991, Oradel et al 1995, Rustin et al 1984) and bevacizumab (Mego et al 2007) have been published. Given the known deregulation of the RB tumor suppressor pathway in GCTs and that nearly all malignant teratomas stain positively for nuclear pRB (Strohmeyer et al 1991, Bartkova et al 2003), treatment of non-resectable malignant teratoma with a CDK 4/6 inhibitor such as LEE011 is a rational approach.

2 Rationale

2.1 Study rationale and purpose

Deregulation of the retinoblastoma tumor suppressor pathway in GCT has been well documented ([Bartkova et al 2003](#)). Upregulation of CDK4 and cyclin D2 is believed to be a central event in GCT tumorigenesis ([Houldsworth et al 1997](#), [Schmidt et al 2001](#)). Inhibition of CDK4/cyclinD1 and CDK6/cyclinD3 complexes prevents the phosphorylation of pRB and renders a cell unable to proceed through cell division. Differentiated NSGCT such as teratocarcinomas and teratomas demonstrate strong expression of pRB ([Strohmeier et al 1991](#), [Bartkova et al 2003](#)).

Treatment for relapsed/refractory/unresectable teratoma remains a high unmet medical need and use of a CDK 4/6 inhibitor such as LEE011 is a rational approach. A phase I study with palbociclib; another selective CDK 4/6 inhibitor, (PD-0332991) included 3 patients with progressive Growing Teratoma Syndrome (GTS) despite maximal surgical excision. Two patients maintained stable disease for 18 and 24 months at the time of the report, and the third had partial response and remained progression free on therapy at 22 months ([Vaughn et al 2009](#)).

The primary purpose of this study is to determine the anti-tumor activity of LEE011 for relapsed, refractory, progressive, incurable teratoma. Targeting the D-Cyclin-CDK axis to inhibit teratoma growth is driven by biological rationale, supporting clinical evidence, and the need for effective targeted therapy in this indication. Evidence of anti-tumor activity in this study will be used to inform future development of LEE011 in other tumors where this pathway may be critical for tumorigenesis.

2.2 Rationale for the study design

This is a randomized double blind (investigator and patient), placebo-controlled, phase II study of LEE011 in patients with progressive relapsed/refractory teratoma for whom standard therapeutic options are not available. The two-arm randomized design minimizes allocation bias, balancing both known and unknown prognostic factors in the assignment of treatment. Blinding will minimize the risk of overstating LEE011 effect. Given the variable growth rate of teratomas, documentation of radiologic progression within 12 weeks prior to enrollment (compared to a prior scan within 1 year) will be required.

A placebo-controlled design with crossover, at time of documented disease progression per RECIST v1.1, permits a more objective assessment of clinical improvement and radiologic response, while at the same time permitting all enrolled patients access to LEE011. There is no accepted standard therapy for patients eligible for enrollment in this study and case reports of individualized regimens are discouraging ([van der Gaast et al 1991](#), [Ornadel et al 1995](#), [Rustin et al 1984](#)). Patients will be randomized 2:1 to the experimental arm in order to

increase the probability of patients receiving active drug upfront and maximize collection of safety data. The presence of a placebo arm will also help to facilitate the evaluation of whether adverse events are related to LEE011. The use of a cross-over design will impact the ability to provide a robust estimate of overall survival, which is acceptable given the exploratory nature of this phase II study.

Preclinical and clinical studies suggest that the vast majority of teratoma have pRB ([Bartkova et al 2003](#)); therefore, pre-screening for pRB status will not be required but will be assessed retrospectively.

